# fMRI Aims:

1. Demonstrate that the UP will attenuate changes resulting from performance on alcohol-word and negative-word Stroop tasks in the activity of frontal-parietal and midbrain regions and the connectivity to networks associated with these regions in AUD subjects. Our working hypothesis is that midbrain activity will be lower in UP participants than those in the TC condition following performance on alcohol and negative emotion Stroop task, which will occur in association with enhanced mid-brain-frontal connectivity and increased synchrony.

2. Demonstrate that the UP attenuates the enhanced regional brain activity and craving- induced by exposure to alcohol related cues in AUD subjects. Our hypothesis is that exposure to alcoholrelated cues will increase brain activity in select limbic and prefrontal areas to a lesser degree in UP completers as compared to UP participants at baseline.

3. Demonstrate that the UP induced changes in brain activity are predictive of reduced ethanol consumption.

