## **General Contact Information**

# **Staff Personnel Contacts and Locations**

# **Research Design**

In this clinical trial, research personnel will further assess the UP's effectiveness in reducing alcohol consumption in participants with comorbid AUD/AXD. Participants will be randomized to one of two conditions: 1) treatment with the UP or 2) treatment with therapist-guided *Take Control* (TC; a psychoeducation-based, alcohol reduction program developed by NIAAA). In addition, a subset of twenty-five participants (UP condition only) will complete functional magnetic resonance scanning (fMRI) to examine the effects of the UP on changes in

brain activity in areas important to regulation of emotional and reward processes implicated in excessive alcohol consumption.

The primary hypotheses are that the UP compared to TC will: 1) be superior in acute symptom reduction from pre- to post-treatment, and 2) evidence greater reductions in percent days heavy drinking, percent days of drinking per week, and alcohol craving.

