# Table 1. Visit Projection Table

#### **Subjects**

A total of 60 participants will be enrolled, with a target male to female ratio of 33:27. This ratio reflects the higher prevalence rates of AUDs in biological men compared to biological women. Forty participants will be randomized to the UP condition and 20 to the Take Control condition. In addition, 25 participants from the UP group will receive two fMRI scans (pre- and post-treatment).

Participants will be recruited via flyers, brochures, lab website and StAR Facebook page, MBTA advertisements, etc. Telephone screenings will determine initial eligibility, and potential research participants will be invited to CARD, located at Boston University, for a more extensive assessment of alcohol use and emotional disorders.

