# **Study Procedures**

Participants will receive 16 treatment sessions over a period of 16 to 21 weeks for UP or 12 treatment sessions in 12 to 16 weeks for TC. Follow-up data will be collected 1- and 6-months post-treatment at in-clinic sessions.

We will offer parking vouchers to participants, as needed, to help defray any costs they may otherwise incur while traveling to our center to complete scheduled assessment appointments. Research personnel will provide up to four parking vouchers (which cost approximately \$10.00 each) to every participant for completion of study assessments.

Note: As of March 18th, 2020, study staff adapted study procedures to operate remotely during the COVID-19 pandemic. These practices have continued into 2021, 2022, 2023, and the remainder of the study. This has included instituting procedures to conduct therapy sessions via telehealth (HIPAA Zoom), collecting data remotely via online services (Qualtrics, Millisecond), and conducting screenings remotely (HIPAA Zoom). IRB approval was obtained for all remote procedures. fMRI procedures were temporarily discontinued due to the COVID-19 pandemic in 2020, but study staff re-initiated scans in 2021 in accordance with BU IRB protocols.

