#### fMRI

Participants that are selected for the fMRI component will also be screened for eligibility in undergoing brain fMRI scans after completing the assessment session at CARD. All enrolled participants must be willing and able to participate in the fMRI component in order to be eligible

to participate in the trial, unless an exception is made by the project director, [name]. About half of the eligible participants randomized to the UP condition will be asked to complete this component of the trial. We will ask all participants in the UP condition to complete the fMRI component until we have reached a sufficient number of participants (with complete scans) to evaluate the fMRI specific aims identified in the approved study protocol.

One scan will occur after randomization but before the first treatment session begins and the second scan will occur within 2 weeks after the last treatment session. Participants will be screened before each scan session for alcohol use (breathalyzers), pregnancy (urine sample, women of childbearing potential only), and illicit substance use (urine sample). Eligible participants may be asked to complete 2 fMRI sessions of 2 hours total. Thirty minutes will be allocated for BAC, pregnancy test (urine sample; women of childbearing potential only), illicit substance use test (urine sample), Alcohol Use Questionnaire (AUQ), and the CILSE safety form. Thirty minutes will be allocated for traveling to CILSE, and prepping materials for the MRI, and 1-hour and a half will be used for the 3 Tesla fMRI scan involving structural imaging (MRI) and functional imaging (fMRI). The participant should complete the AUQ both before and after the fMRI scans in Qualtrics.

The fMRI scans include a resting-state scan (no task involved), a cognitive (Stroop) task, an alcohol cue reactivity task and an Event Based Reappraisal Task. The Stroop, alcohol cue, and Event Based Reappraisal scans involve presentation of visual images to participants while they are in the scanner. No contrast agent or invasive procedures are used. Only personnel trained in working in high magnetic field environments will work on this project. Imaging data will be analyzed on secure networks using only encrypted files. All data obtained will be coded to protect participants' privacy and confidentiality.

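### fMRI Aims 2 and 3 credit brain changes to UP, but only UP participants are scanned, so the data can show change and association within UP and not a UP effect

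*Combined protocol and SAP*

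**What the plan says.** Under the heading fMRI Aims, Aim 2 is to "Demonstrate that the UP attenuates the enhanced regional brain activity" and craving that alcohol cues provoke. Its hypothesis is that cues will raise activity "to a lesser degree in UP completers as compared to UP participants at baseline". Aim 3 is to "Demonstrate that the UP induced changes in brain activity are predictive of reduced ethanol consumption"; it names no comparator. The Research Design section says scanning is done "to examine the effects of the UP on changes in" brain activity.

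The sampling is explicit. The Subjects section says "25 participants from the UP group will receive two fMRI scans (pre- and post-treatment". Research Design, Treatment Conditions, Randomization, the fMRI section and the Compensation Schedule all confine scanning to the UP arm. The first scan falls between randomisation and session 1. Study Procedures gives "16 treatment sessions over a period of 16 to 21 weeks for UP", and the fMRI section adds that "the second scan will occur within 2 weeks after the last treatment session".

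The document describes no scanned TC participants, no untreated or healthy scanned group and no repeat baseline scan. It gives no analysis method for Aims 2 and 3 and no caveat about attribution.

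**The concern.** Aims 2 and 3 can be estimated from the planned data. The difficulty is that the conclusion they name does not follow from the estimate. Four months or more pass between scans. Participants enter because of recent heavy drinking and a wish to stop or cut down, so some would drink less under any treatment or none. They also see the alcohol-cue task a second time. A fall in cue-related activity is what UP should produce if it works, and also what these other influences could produce if it does not.

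The trial randomises against therapist-delivered TC, which for the drinking outcomes holds time and therapist contact roughly in common. The imaging aims give up that comparison but keep causal language. If the plan is followed as written, a significant before-after fall would be reported as a demonstrated effect of UP on the brain.

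**Working it through.** **What is compared with what**

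| Item | Wording of the aim | What the scans allow |
|---|---|---|
| Aim 2 | UP reduces cue-related activity | Post minus pre, UP only |
| Aim 3 | Changes caused by UP predict less drinking | Correlation of two changes, UP only |
| Research Design | Effects of UP on brain activity | Change during UP |

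In each row the left-hand claim needs an estimate of what would have happened without UP. No scanned group supplies one.

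**Aim 2, illustration**

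The plan gives no effect size, standard deviation, alpha or power for the imaging aims, so there is no figure to reproduce.

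Inputs: n = 25 pairs (Subjects section). Assumed: one paired t-test, two-sided 5%, true UP effect zero, and a non-UP fall of d standard deviations of the change score.

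Formula: P(significant fall) = 1 − F(t_crit; df = n − 1, non-centrality = d√n), where F is the non-central t distribution. For n = 25, √n = 5 and t_crit = 2.064.

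| d (assumed) | Non-centrality, n = 25 | P, 25 pairs | P, 20 pairs (assumed loss of 5) |
|---|---|---|---|
| 0 | 0 | 2.5% | 2.5% |
| 0.2 | 1.0 | 15.9% | 13% |
| 0.4 | 2.0 | 48.4% | 40% |
| 0.6 | 3.0 | 82.1% | 72% |

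For contrast, a two-sample test was simulated on change scores, with 25 scanned UP and 12 or 20 scanned TC participants and the same drift in both arms (0, 0.5 or 0.8; 20,000 runs each). The false-positive rate stayed between 2.3% and 2.6%. The inflation therefore comes from the missing comparator.

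**Aim 3**

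Adding the same constant to every participant's change leaves a correlation unchanged, so a uniform repeat-scan shift cannot produce the Aim 3 result. A factor that varies between people can. Suppose a non-UP cause, or drinking less acting on the brain, gives a true correlation ρ between the two changes. With n = 25, t = r√(23/(1 − r²)) must exceed 2.069, that is r > 2.069/√(23 + 2.069²) = 0.396. Simulation (20,000 runs) gives a significant positive association in about 31%, 75% and 91% of runs for assumed ρ of 0.3, 0.5 and 0.6. Such an association would be real. What remains unsupported is calling the brain changes induced by UP.

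**The case against.** **The comparison is disclosed.** Aim 2 states that it sets UP completers against UP baseline, and nothing is presented as a between-arm result. That is true, and it limits the point to what is concluded from the data. But the aim is to demonstrate an effect, and no caveat accompanies it. The plan shows such caution elsewhere: Data Analysis Aim 4 says its parallel-process models are not formal tests of mechanism.

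**The details may sit elsewhere.** The document refers to an approved study protocol for the fMRI aims and to a data analysis section in the grant. Neither is available here, and a caveat may exist there. The aims as worded in this document would still need to agree with it.

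**It has the same root as Aim 1.** Aim 1 contrasts UP with TC, which is never scanned. Correcting Aim 1 would leave Aims 2 and 3 as they are.

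A reader might also infer more than the documents support:

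- *That nothing in the design removes scanner effects.* The cue task shows neutral as well as alcohol images in each session, so an alcohol-minus-neutral contrast can remove general scanner effects. Cue-specific habituation and time effects remain.
- *That regression to the mean acts directly on the scans.* Entry selects on drinking and not on brain activity, so any effect is indirect. The plan also keeps out of active treatment people whose drinking halved between phone screen and in-person screening, or who were already at safe levels, which removes some early regression.
- *That reused pictures explain the Aim 2 result.* The instruction to keep one picture set before and after belongs to the reappraisal task, which no fMRI aim names.
- *That the percentages apply to both aims or are this trial's error rates.* They apply to Aim 2 only, and rest on assumed drift and one uncorrected test, although the aim concerns several brain areas.

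**Conclusion.** The concern holds in limited form. With two scans per person in the UP arm alone, Aims 2 and 3 can describe change, and its association with drinking, among people who received UP. They cannot attribute either to UP, because time, cue-specific habituation and drinking reduction that would occur anyway are not separable from it.

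The size cannot be fixed from the documents. For Aim 2, assumed non-UP falls of 0.2 to 0.6 turn a nominal 2.5% into 16% to 82% on a single paired test with 25 pairs. If there is no drift, there is no inflation. For Aim 3 the defect is one of interpretation: the association may be real, but its attribution to UP is unsupported. The primary drinking comparison is unaffected. The wording should be changed before imaging results are reported.

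**What to change.** 1. Restate Aim 2 as change within UP participants, from before to after treatment, in the alcohol-minus-neutral contrast (post minus pre), in participants with both scans. Using the same people at both times also avoids setting completers against a wider baseline group.
2. Restate Aim 3 as the association, within UP, between change in brain activity and change in drinking.
3. Reword the Research Design sentence to match, and remove from all three places the language that attributes change to UP.
4. Add one sentence stating that cue-specific habituation and time effects cannot be separated from UP in this design, and that regression to the mean may contribute indirectly through selection on drinking.

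This needs no new scans, participants or procedures. The cost is a weaker stated imaging claim. Scanning TC participants would be needed to keep the causal claim, but that is a different and larger study component and is not required for this correction.

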## **StAR2 Grant Information**

Title: Efficacy Evaluation of Transdiagnostic CBT for Comorbid Alcohol Use and Anxiety Disorders Granting Agency: National Institute on Alcohol Abuse and Alcoholism Date of Submission: 09/01/2017 Ending Date: 08/31/2022 NIAAA Grant Number: 1R01 AA023676

# **Graduate Research Assistants**

Graduate research assistants (GRA) are doctoral students in the Clinical Psychology Program at Boston University. These students will serve a number of important functions, including assessing diagnostic criteria for eligibility into the project (both are trained to "gold standard" criterion for reliability).

#### **Research Assistants**

Research assistants will be responsible for scheduling participants, conducting phone screens, running study sessions, data management, IRB related tasks, and MRI sessions.

## **General Contact Information**

# **Staff Personnel Contacts and Locations**

# **Research Design**

In this clinical trial, research personnel will further assess the UP's effectiveness in reducing alcohol consumption in participants with comorbid AUD/AXD. Participants will be randomized to one of two conditions: 1) treatment with the UP or 2) treatment with therapist-guided *Take Control* (TC; a psychoeducation-based, alcohol reduction program developed by NIAAA). In addition, a subset of twenty-five participants (UP condition only) will complete functional magnetic resonance scanning (fMRI) to examine the effects of the UP on changes in

brain activity in areas important to regulation of emotional and reward processes implicated in excessive alcohol consumption.

The primary hypotheses are that the UP compared to TC will: 1) be superior in acute symptom reduction from pre- to post-treatment, and 2) evidence greater reductions in percent days heavy drinking, percent days of drinking per week, and alcohol craving.

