# **Study Overview**

## **Data Analysis Aims:**

1. Demonstrate that Unified Protocol (UP) treatment reduces alcohol consumption relative to Take Control (TC), as measured by our primary outcome measure, mean number of drinks consumed per week.

Comparisons will be made for data obtained for the treatment period for the two conditions. Specifically, the hypothesis that participants in the UP condition will evidence greater reductions in our primary efficacy measure (mean weekly number of standard drinks) than participants receiving TC will be examined using conditional latent growth models (LGM), modeled using MPlus 7.0 (Muthén & Muthén, 1998-2012). Research personnel will examine changes in the weekly mean number of drinks consumed per day over the course of treatment (i.e., study sessions 1 to 16). They will also examine whether the proportion of subjects achieving safe levels of drinking (males = 2 drinks per day; females = 1 drink per day) is significantly greater in the UP condition than in the TC group (guidelines from USDA, 2010). This will be done by calculating odds ratio effect sizes (with 95% confidence interval) contrasting safe levels of drinking in the UP vs. TC groups.

2. Demonstrate that the UP, relative to TC, reduces alcohol intake on other measures of alcohol consumption and evaluate the extent to which this also leads to a comparative decrease in measures of craving.

Conditional LGM will be used to test the hypothesis that UP will both demonstrate greater reductions in the secondary efficacy measures of percent days heavy drinking per week (defined as more than 3 drinks per drinking day for biological women and more than 4 drinks per drinking day for biological men [NIAAA guidelines]), percent days of drinking per week, and in alcohol craving (as assessed by the Alcohol Urge Questionnaire and the Obsessive Compulsive drinking scale) than the TC condition.

3. Demonstrate that the UP results in greater reductions in anxiety and depression as measured by the SIGH-A, SIGH-D, ODSIS, and OASIS than TC, and that there will be a correlation between these reductions and the decreases seen in mean weekly number of standard drinks consumed per day, percent days heavy drinking per week, percent days drinking per week, and alcohol craving.

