This will be examined using conditional and parallel-process LGC. Research personnel will first conduct separate LGM for anxiety and depression. Then they will conduct a series of parallel process LGM to examine how changes in anxiety and depression relate to changes in the primary and three secondary alcohol outcomes. Separate parallel process LGM will be conducted for

each alcohol outcome, and both anxiety and depression will be included in each parallel process LGM.

4. Demonstrate that the UP results in greater changes in temperament (e.g., reductions in neuroticism) and emotion regulation (e.g., experiential avoidance) variables associated with anxiety and depression than TC, and that these changes are associated with changes in anxiety and depression.

This will be examined using LGM models similar to those described above. These parallel process LGM will not provide formal tests of mechanisms of change as these models will examine concurrent changes. If the results from these models are promising, they will be followed by models that permit more fine-grained examinations of temporal dependencies of change.

5. Demonstrate that the UP will reduce impulsive and risk-taking behaviors. Our working hypothesis is that the UP will decrease risk taking behavior as assessed using the Cambridge Gambling Task and the Balloon Analog Risk Task, and impulsivity as measured by the Go/NoGo and the Continuous Performance Test (CPT).

Repeated measures mixed models analysis will be used to analyze data obtained for prerandomization and week 16 data for the Cambridge Gambling Task, the Balloon Analog Risk Task, the Go/NoGoTask, the CPT, and Go/No Go. Model generated group least square means values for week 16 will be compared using student t-tests.

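### Research Design puts three outcomes that the Data Analysis Aims call secondary under its primary hypotheses, and does not name drinks per week

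*Combined protocol and SAP*

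**What the plan says.** Two current sections of the combined protocol and SAP rank the outcomes.

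- **Study Overview, Data Analysis Aims.** Aim 1 compares UP with TC on alcohol consumption "as measured by our primary outcome measure, mean number of drinks consumed per week", to be analysed with conditional latent growth models. Aim 2 expects UP to show "greater reductions in the secondary efficacy measures of percent days heavy drinking per week" and goes on to list percent days drinking and craving, the last "as assessed by the Alcohol Urge Questionnaire and the Obsessive Compulsive drinking scale". The analysis text for Aim 3 confirms the count when it describes how "changes in anxiety and depression relate to changes in the primary and three secondary alcohol outcomes".
- **Research Design.** The section opens with the general purpose of assessing UP's "effectiveness in reducing alcohol consumption in participants with comorbid AUD/AXD". It then says: "The primary hypotheses are that the UP compared to TC will: 1) be superior in acute symptom reduction from pre- to post-treatment". The second primary hypothesis is that UP will "evidence greater reductions in percent days heavy drinking, percent days of drinking per week, and alcohol craving". Drinks per week is not mentioned.

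Nothing in the documents provided says which statement governs, or defines the symptom reduction in hypothesis 1.

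**The concern.** A primary hypothesis is normally tested on the primary outcome. In Research Design the only measures named under that heading are the three that the Aims rank as secondary, and the outcome that the Aims rank as primary is absent. The other hypothesis under the heading has no instrument attached.

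At stake is what may later be called a primary success. If drinks per week showed no difference but craving or percent days heavy drinking did, an author could cite Research Design and report a primary hypothesis as supported. With 60 participants split 40 to 20, the ranking of outcomes should not be left open to choice after the results are known.

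**Working it through.** **1. The two rankings side by side**

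| Measure | Data Analysis Aims | Research Design |
|---|---|---|
| Mean drinks per week | Primary (Aim 1) | Not named |
| Percent days heavy drinking | Secondary (Aim 2) | Under primary hypothesis 2 |
| Percent days drinking | Secondary (Aim 2) | Under primary hypothesis 2 |
| Craving (AUQ, OCDS) | Secondary (Aim 2) | Under primary hypothesis 2 |
| Acute symptom reduction | Not a named outcome | Primary hypothesis 1, no instrument |

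The sentence in Aim 2 could be read as setting craving apart from the secondary measures. The later count of one primary and three secondary alcohol outcomes settles that craving is the third secondary.

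**2. What hypothesis 1 could mean**

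- *Aim 1 in loose wording.* Research Design opens with alcohol consumption, and its two hypotheses run parallel to Aims 1 and 2. This is the more likely reading.
- *Anxiety and depression.* Aim 3 expects "greater reductions in anxiety and depression as measured by the SIGH-A, SIGH-D, ODSIS, and OASIS than TC". The document's use of the word symptoms does not decide the matter: it is used for anxiety and depression in the SIGH-A and SIGH-D training text, for alcohol withdrawal in the CIWA description, and generically in the CGI description.

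On either reading, the three Aim 2 measures remain under a primary heading.

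**3. Illustration of size**

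The documents give no figure to reproduce: no test alpha, success rule or multiplicity rule is stated. The section on premature termination refers to a Data Analysis Section of the grant, which is not included. The inputs below are therefore assumptions.

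- Each test is two-sided at 0.05. The hypotheses are directional in favour of UP, so only the half in UP's favour, 0.025, can produce a false win.
- Number of tests: 4 (hypothesis 1 as one measure, percent days heavy drinking, percent days drinking, craving), or 5 if AUQ and OCDS are tested separately.
- No true effect on any measure.

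If all hypotheses must succeed, as the joining word "and" in Research Design allows, the false-win rate cannot exceed that of a single test, 2.5%.

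If any one win for UP counted, with independent tests, the rate is 1 − 0.975^k:

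- k = 1: 2.5%
- k = 4: 1 − 0.975^4 = 1 − 0.9037 = 9.6%
- k = 5: 1 − 0.975^5 = 1 − 0.8811 = 11.9%

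Positive correlation lowers these. With equicorrelated normal test statistics, a correlation of 0.5 gives about 7.8% (k = 4) and 9.1% (k = 5); a correlation of 0.8 gives 5.7% and 6.4%.

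**4. The metric itself**

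Aim 1 states its measure per week, but also describes it as a weekly average of daily drinks. Aim 3 attaches a per-day qualifier to the weekly count. This is largely a rescaling and need not change a test, but a rewrite that simply points to Aim 1 would carry the mixed wording forward.

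**The case against.** The strongest defence is that the primary outcome is not in doubt. The Aims are the analysis text: they name drinks per week as primary twice, attach a model to it, label the Aim 2 measures secondary, and repeat the one-plus-three count. Research Design is a short narrative with no analysis attached, and a statistician working from the Aims would test the right thing. That stands, and it is why no planned test changes. It does not remove the mismatch, because both texts are current and neither defers to the other.

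Three stronger readings are tempting and should be resisted.

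- A reader might infer that the trial has no defined primary outcome. It has one, in Aim 1.
- A reader might infer a large inflation of error, for example 18.5% from 1 − 0.95^4. That counts significant results in both directions, whereas a result favouring TC cannot support these hypotheses. It also needs an any-one-wins rule that the documents do not state; the unseen grant section may hold a success rule.
- A reader might infer that hypothesis 1 means the four Aim 3 scales, and so count seven or eight primary tests. The text does not establish this, and the parallel with Aims 1 and 2 points the other way.

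Nor does anything in the documents show an intention to claim success on secondary measures. The reporting risk is an opening left by the wording.

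**Conclusion.** The inconsistency is real and can be checked from the text alone: three measures ranked secondary in the Aims are placed under the primary hypotheses in Research Design, drinks per week is missing there, and one primary hypothesis has no instrument. The confidence is high for that mismatch and does not depend on any number.

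The consequence is limited to reporting. Its size runs from no inflation, if all hypotheses must succeed, to a false-win rate of about 9.6% or 11.9% in place of 2.5%, if any single win for UP were accepted. The upper figures rest on an assumed alpha, an assumed success rule, independence, and hypothesis 1 being a single measure. This should be fixed, as a modest correction of wording.

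**What to change.** 1. Rewrite the last paragraph of Research Design to state one primary hypothesis: UP against TC on mean standard drinks per week.
2. Use that single metric throughout the Data Analysis Aims, replacing the per-day variants in Aims 1 and 3.
3. List percent days heavy drinking, percent days drinking and craving (AUQ and OCDS) as secondary.
4. Delete the acute symptom reduction clause, or tie it to named secondary measures such as the Aim 3 scales.
5. Submit the change as an IRB amendment, as the Amendments section requires, and record its date relative to access to outcome data by arm. Study Procedures describes remote working as continuing into 2023, so an undated change could be read as made after results were seen.

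The cost is a wording amendment, with no new data and no change to a planned analysis. The downside for the sponsor is giving up primary claims on the secondary measures.
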